7.7 Overall Type I Error Control

Overall Type I error control is not planned in this Phase 2a study.

7.8 Sample Size Determination

The planned sample size is approximately 40 subjects.

A meta-analysis for historical placebo data from UC studies for tofacitinib (OCTAVE1/2), upadacitinib (Phase 2b and Phase 3; data on file), and ustekinumab (UNIFI) gives CCI [REDACTED] improvement rate at Week 8. A prior placebo distribution that matches this overall rate and has a variance close to the variance of the rate estimate from CCI [REDACTED]. The prior distribution for the ABBV-668 treatment group is set to Jeffreys non-informative prior Beta (0.5, 0.5). Assuming a response rate increase of 30% in the ABBV-668 group compared to historical placebo, a sample size of 40 subjects will provide more than 90% probability to demonstrate that the posterior probability of rate difference (ABBV-668 vs. external placebo) > 0 is larger than 90%. The external

placebo response may be updated if new placebo data from similar trials become available before the Primary Analysis database lock.

8 ETHICS

8.1 Independent Ethics Committee/Institutional Review Board

The protocol, informed consent form(s), recruitment materials, and all subject materials will be submitted to the IEC/IRB for review and approval. Approval of both the protocol and the informed consent form(s) must be obtained before any subject is enrolled. Any amendment to the protocol will require review and approval by the IEC/IRB before the changes are implemented to the study. In addition, all changes to the consent form(s) will be IEC/IRB approved.

8.2 Ethical Conduct of the Study

The study will be conducted in accordance with the protocol, Operations Manual, International Council for Harmonisation (ICH) guidelines, applicable regulations, and guidelines governing clinical study conduct and the ethical principles that have their origin in the Declaration of Helsinki. Responsibilities of the investigator are specified in [Appendix B](#). Investigators should notify AbbVie if any urgent safety measures are taken to protect the subjects against any immediate hazard.

8.3 Subject Confidentiality

To protect subjects' confidentiality, all subjects and their associated samples will be assigned numerical study identifiers or "codes." No identifiable information will be provided to AbbVie.

9 SOURCE DOCUMENTS AND CASE REPORT FORM COMPLETION

The investigator is responsible for ensuring the accuracy, completeness, legibility, and timeliness of the data reported. All source documents should be attributable, legible, contemporaneous, original, accurate, and complete to ensure accurate interpretation of data. Clinical site monitoring is conducted to ensure that the rights and well-being of human subjects are protected, that the reported trial data are accurate, complete, and verifiable, and that the conduct of the trial is in compliance with the currently approved protocol, ICH Good Clinical Practice (GCP), and applicable local regulatory requirement(s). During the COVID-19 pandemic and geo-political conflict in Ukraine and surrounding impacted regions, remote data review/verification may be employed if allowed by the local regulatory authority, IRB/IEC, and the study site.

10 DATA QUALITY ASSURANCE

AbbVie will ensure that the clinical trial is conducted with a quality management system that will define quality tolerance limits to ensure human subject protection and reliability of study results. Data will be

generated, documented, and reported in compliance with the protocol, ICH GCP, and applicable regulatory requirements.

11 START AND COMPLETION OF THE STUDY

The start-of-study is defined as the date of the first site activated.

The end-of-study is defined as the date of end of study participation by the last subject in the last country where the study was conducted.

APPENDIX A. STUDY-SPECIFIC ABBREVIATIONS AND TERMS

Abbreviation	Definition
5-ASA	5-aminosalicylic acid
6-MP	6-mercaptopurine
6-TGN	6-thioguanine nucleotide
ADA	antidrug antibody
AE	adverse event
AESI	adverse event of special interest
Ag	antigen
ALT	alanine transaminase
AST	aspartate transaminase
AZA	azathioprine
BID	twice a day
BM	biomarker
BP	blood pressure
CD	Crohn's disease
CFR	Code of Federal Regulations
CL/F	apparent clearance or apparent oral clearance
CRP	C-reactive protein
C-SSRS	Columbia-Suicide Severity Rating Scale
CTCAE	Common Terminology Criteria for Adverse Events
CYP	cytochrome P450
CYP3A	cytochrome P450 3A isoform subfamily
DNA	deoxyribonucleic acid
DTP	direct-to-patient
EC	ethics committee
ECG	electrocardiogram
eCRF	electronic case report form
EDC	electronic data capture
eGFR	estimated glomerular filtration rate
EIM	extraintestinal manifestation
ESS	Endoscopic Subscore
EU	European Union

Abbreviation	Definition
FACIT	Functional Assessment of Chronic Illness Therapy
FCP	fecal calprotectin
FDA	Food and Drug Administration
FSH	follicle-stimulating hormone
GCP	Good Clinical Practice
GR	glucocorticoid receptor
HAQ-DI	Health Assessment Questionnaire Disability Index
HBV	hepatitis B virus
HCV	hepatitis C virus
HIV	human immunodeficiency virus
hs-CRP	high sensitivity C-reactive protein
IBD	inflammatory bowel disease
IBDQ	Inflammatory Bowel Disease Questionnaire
IBD-U	inflammatory bowel disease-unclassified
ICH	International Council for Harmonisation
IEC	independent ethics committee
IEC/IRB	Independent Ethics Committee/Institutional Review Board
IHC	immunohistochemistry
IM	intramuscular
IMP	Investigational Medicinal Product
INR	international normalized ratio
IRB	institutional review board
IRT	interactive response technology
ITT	Intent-to-Treat
IU	international unit
IUD	intrauterine device
IUS	Intrauterine hormone-releasing system
IV	intravenous
JAK	Janus kinase
LDA	low disease activity
MA	marketing authorization
MedDRA	Medical Dictionary for Regulatory Activities
mRNA	messenger ribonucleic acid

Abbreviation	Definition
MTX	methotrexate
NAb	neutralizing antibody
NCI	National Cancer Institute
NCS	not clinically significant
NMSC	nonmelanoma skin cancer
NRI	Non-Responder Imputation
NRI-MI	Non-Responder Imputation incorporating multiple imputation
OR	odds ratio
PBMC	peripheral blood mononuclear cell
PCR	polymerase chain reaction
PCS	potentially clinically significant
PD visit	Premature Discontinuation visit
PGA	Physicians' Global Assessment
PK	Pharmacokinetics
PO	orally
PRO	patient-reported outcome
PT	preferred term
QOL	quality of life
QTcF	QT interval corrected for heart rate using Fridericia's formula
RA	regulatory affairs
RBC	red blood cell
RBS	Rectal Bleeding Subscore
RIPK1	Receptor interacting serine/threonine-protein kinase 1
RNA	ribonucleic acid
RSI	Reference Safety Information
S1P	sphingosine-1-phosphate
SAE	serious adverse event
SAP	Statistical Analysis Plan
SAR	serious adverse reaction
SC	subcutaneous
SFS	Stool Frequency Subscore
SOC	system organ class
SUSAR	Suspected Unexpected Serious Adverse Reaction

Abbreviation	Definition
TB	tuberculosis
TEAE	treatment-emergent adverse event
TLR	toll-like receptor
TNF	tumor necrosis factor
UC	ulcerative colitis
ULN	upper limit of normal
V/F	apparent volume of distribution

APPENDIX B. RESPONSIBILITIES OF THE INVESTIGATOR

Protocol M21-446: A Single-Arm, Open-Label Study to Evaluate the Efficacy and Safety of ABBV-668 in Subjects with Moderate to Severe Ulcerative Colitis

Protocol Date: 03 March 2023

Clinical research studies sponsored by AbbVie are subject to the International Council for Harmonisation of Technical Requirements for Pharmaceuticals for Human Use (ICH) Good Clinical Practices (GCP) and local laws and regulations and guidelines governing the study at the site location. In signing the Investigator Agreement, the investigator is agreeing to the following:

1. Conducting the study in accordance with ICH GCP, the applicable regulatory requirements, current protocol and operations manual, and making changes to a protocol only after notifying AbbVie and the appropriate Institutional Review Board (IRB)/Independent Ethics Committee (IEC), except when necessary to protect the subject from immediate harm.
2. Personally conducting or supervising the described investigation(s).
3. Informing all subjects, or persons used as controls, that the drugs are being used for investigational purposes and complying with the requirements relating to informed consent and ethics committees (e.g., IEC or IRB) review and approval of the protocol and its amendments.
4. Reporting complaints that occur in the course of the investigation(s) to AbbVie.
5. Reading the information in the Investigator's Brochure/safety material provided, including the instructions for use and the potential risks and side effects of the investigational product(s).
6. Informing all associates, colleagues, and employees assisting in the conduct of the study about their obligations in meeting the above commitments.
7. Maintaining adequate and accurate records of the conduct of the study, making those records available for inspection by representatives of AbbVie and/or the appropriate regulatory agency, and retaining all study-related documents until notification from AbbVie.
8. Maintaining records demonstrating that an ethics committee reviewed and approved the initial clinical protocol and all of its amendments.
9. Reporting promptly (within one (1) calendar day to AbbVie, the ethics committees/institutional review boards (as required) and other appropriate individuals (e.g., coordinating investigator, institution director):
 - All changes in the research activity and all unanticipated problems involving risks to human subjects or others

APPENDIX D. ACTIVITIES SCHEDULE

The following table shows the required activities for each visit. The individual activities are described in detail in the **Operations Manual** ([Appendix F](#)). Allowed modifications due to COVID-19 and/or the geo-political conflict in Ukraine and surrounding impacted regions are detailed in the Operations Manual.

Activity	Screening	16 Week Open Label Treatment Period (± 3 days)										PD Visit (± 3 days)	Unscheduled Visit	30- Day Follow-Up (± 7 days)
		Baseline	Week 2	Week 4	Week 6	Week 8	Week 10	Week 12	Week 14	Week 16				
INTERVIEWS & QUESTIONNAIRES														
Informed consent	✓													
Eligibility criteria	✓	✓												
Medical/surgical history	✓	✓												
Prior and concomitant medication	✓	✓	✓	✓	✓	✓	✓	✓	✓	✓	✓	✓	✓	✓
IBDQ		✓				✓				✓				
FACIT-F		✓				✓				✓				
C-SSRS	✓	✓				✓				✓	✓			
PGIS		✓	✓	✓	✓	✓	✓	✓	✓	✓	✓			
PGIC			✓	✓	✓	✓	✓	✓	✓	✓	✓			
Monitor Adverse Events	✓	✓	✓	✓	✓	✓	✓	✓	✓	✓	✓	✓	✓	✓
Latent TB risk assessment form	✓													
Review and document continued compliance with pregnancy avoidance recommendations in the source records as appropriate	✓	✓	✓	✓	✓	✓	✓	✓	✓	✓	✓	✓	✓	✓
Provide stool kit	✓	✓			✓		✓		✓					
Dispense Daily Subject Diary	✓													
Daily Subject Diary review		✓	✓	✓	✓	✓	✓	✓	✓	✓	✓	✓	✓	
LOCAL LABS & EXAMS														
Endoscopy	✓						✓				✓			
Chest X-Ray	✓													

Activity	Screening	16 Week Open Label Treatment Period (± 3 days)											PD Visit (± 3 days)	Unscheduled Visit	30- Day Follow-Up (± 7 days)
		Baseline	Week 2	Week 4	Week 6	Week 8	Week 10	Week 12	Week 14	Week 16					
12-lead ECG	✓			✓						✓		✓			
Height	✓														
Weight	✓	✓				✓				✓					
Vital signs	✓	✓	✓	✓	✓	✓	✓	✓	✓	✓		✓			
Physical examination	✓	✓				✓				✓		✓			
Neurological examination	✓	✓	✓	✓	✓	✓		✓		✓		✓			
Urine pregnancy test (females of childbearing potential)		✓	✓	✓	✓	✓	✓	✓	✓	✓					✓
CENTRAL LABS															
Estimated glomerular filtration rate (eGFR)	✓														
Optional biologic drug level	✓														
Serum pregnancy test (females of childbearing potential)	✓														
FSH (if needed to confirm postmenopausal status)	✓														
QuantiFERON-TB Gold test (and/or local PPD skin test)	✓														
hs-CRP, clinical chemistry, hematology (CBC)	✓	✓	✓	✓	✓	✓		✓		✓		✓			
Urinalysis	✓											✓			
Lipid test	✓											✓			
HBV, HCV, and HIV Screening	✓														
Intestinal biopsies: histology	✓					✓				✓					
Stool sample (C. difficile toxin)	✓														

Activity	Screening	16 Week Open Label Treatment Period (± 3 days)										PD Visit (± 3 days)	Unscheduled Visit	30- Day Follow-Up (± 7 days)
		Baseline	Week 2	Week 4	Week 6	Week 8	Week 10	Week 12	Week 14	Week 16				
Stool sample (Fecal calprotectin)		✓	✓			✓		✓		✓		✓	✓	
Blood samples for CCI and ABBV-668 PK assays		✓	✓		✓	✓				✓		✓	✓	
BIOMARKER RESEARCH SAMPLES														
RIPK1 Target Engagement (Two baseline samples needed)		✓	✓	✓		✓				✓				
Pathway Engagement/PD: CCI (Two baseline samples needed)		✓	✓	✓		✓				✓				
PBMC		✓				✓				✓				
Serum		✓	✓	✓		✓				✓	✓			
Plasma		✓	✓	✓		✓				✓	✓			
Stool		✓	✓			✓		✓		✓	✓			
Whole blood PaxGene RNA		✓	✓	✓		✓				✓	✓			
Optional biomarker sample: Whole blood DNA (Baseline or anytime during study)		✓												
Intestinal biopsies: RNAlater	✓					✓				✓				
Intestinal biopsies: FFPE for MOA (e.g., CCI)	✓					✓				✓				
Rx TREATMENT														
Adapted Mayo/Full Mayo Score		✓				✓				✓				
Partial Mayo/Adapted Partial Mayo Score		✓	✓	✓	✓	✓	✓	✓	✓	✓	✓	✓	✓	
Study drug dispensing/administration		✓		✓		✓		✓		✓				

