4 INVESTIGATIONAL PLAN

4.1 Overall Study Design and Plan

Study M21-446 is a Phase 2a, multicenter, open-label proof of concept study to investigate the efficacy and safety of ABBV-668 in subjects with moderate to severe UC. The study contains a 30-day screening period, 16-week treatment period, and a 30-day follow up period from the last dose of study drug.

Approximately 40 subjects will be enrolled in this study.

[figure not shown]
An endoscopy is required at Screening and at Week 8 to evaluate endoscopic improvement. To explore the time course of ABBV-668 efficacy, subjects will continue through Week 16. An endoscopy will be performed at Week 16 for subjects:

- Who have an endoscopic subscore of ≥ 1 at the Week 8 endoscopy; or
- Who have an endoscopic subscore of 0 at the Week 8 endoscopy AND have subsequent worsening of their disease (as assessed by the investigator) after the Week 8 endoscopy.

The schematic of the study is shown in [Figure 1](#). Details regarding study procedures are provided in the Operations Manual ([Appendix F](#)).

See Section [5.1](#) for information regarding eligibility criteria.

Figure 1. Study Schematic

BID = twice a day

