5.6 Follow-Up After Subject Discontinuation of Study Drug or from Study

To minimize missing data for efficacy and safety assessments, subjects who prematurely discontinue study drug treatment should continue to be followed for all regularly scheduled visits, unless subjects have decided to discontinue the study participation entirely (withdrawal of informed consent). Subjects should be advised on the continued scientific importance of their data even if they discontinue treatment with study drug early.

If a subject prematurely discontinues study participation (withdrawal of informed consent), the procedures outlined for the Premature Discontinuation visit (PD visit) should be completed as soon as possible, preferably within 2 weeks. In addition, if subject is willing, a 30-day follow-up phone call after

the last dose of study drug may be completed to ensure all treatment-emergent AEs/serious adverse events (SAE) have been resolved.

If a subject withdraws from study follow up or withdraws permission for the collection of their personal data, the study staff may still use available public records to obtain information about survival status only, as appropriate per local regulations.

All subjects should be referred to their treating physician for appropriate management for UC following completion of the study.

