Such an event can result from use of the drug as stipulated in the protocol or labeling, as well as from "special situations" such as accidental or intentional overdose, medication error, occupational or accidental exposure, off-label use, drug abuse, drug misuse, or drug withdrawal, all which must be reported whether associated with an AE or not. Any worsening of a pre-existing condition or illness is considered an AE. Worsening in severity of a reported AE should be reported as a new AE. Laboratory abnormalities and changes in vital signs are considered to be AEs only if they result in discontinuation from the study, necessitate therapeutic medical intervention, meets protocol-specific criteria (see Section 6.2 regarding toxicity management), and/or if the investigator considers them to be AEs.

The investigators will monitor each subject for clinical and laboratory evidence of AEs on a routine basis throughout the study. All AEs will be followed to a satisfactory conclusion.

An elective surgery/procedure scheduled to occur during a study will not be considered an AE if the surgery/procedure is being performed for a pre-existing condition and/or the surgery/procedure has

been pre-planned prior to study entry. However, if the pre-existing condition deteriorates unexpectedly during the study (e.g., surgery performed earlier than planned), then the deterioration of the condition for which the elective surgery/procedure is being done will be considered an AE.

If any of the following events are reported, then the following supplemental report must be completed.

Event	Supplemental Report
Cardiac events Myocardial infarction or unstable angina Heart failure Cerebral vascular accident and transient ischemic attack Cardiovascular procedures (SAE Supplemental Procedure eCRF)	Cardiovascular (Cardiac) Adverse Event eCRF MI and Unstable Angina Adverse Event eCRF Heart Failure Adverse Event eCRF Cerebral Vascular Accident and Transient Ischemic Attack AE eCRF Combination Thrombotic Event AE eCRF Arrhythmia AE eCRF
Discontinuation or interruption of study drug due to a hepatic-related AE A hepatic-related SAE ALT/AST > 8 × ULN or ALT/AST > 3 × ULN with a total bilirubin > 2 × ULN	Hepatic AE eCRF
Renal impairment Renal dysfunction Renal failure Serum creatinine > 2.0 mg/dL	Renal AE Renal Supplemental Local Labs Renal Supplemental Procedures Renal Abnormal Lab Value Supplemental
Herpes zoster infection	Herpes zoster eCRF
Any malignancy	Malignancy eCRF

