All adverse events reported from the time of study drug administration until 30 days after discontinuation of study drug administration will be collected, whether solicited or spontaneously reported by the subject. In addition, study procedure-related serious and nonserious adverse events will be collected from the time the subject signs the study-specific informed consent.

The following definitions will be used for Serious Adverse Reactions (SAR) and Suspected Unexpected Serious Adverse Reaction (SUSAR):

SAR	Defined as all noxious and unintended responses to an IMP related to any dose administered that result in an SAE as defined above.
SUSAR	Refers to individual SAE case reports from clinical trials where a causal relationship between the SAE and the IMP was suspected by either the sponsor or the investigator, is unexpected (not listed in the applicable Reference Safety Information), and meets one of the above serious criteria.

AbbVie will be responsible for SUSAR reporting for the Investigational Medicinal Product (IMP) in accordance with global and local requirements.

AEs will be monitored throughout the study to identify any of special interest that may indicate a trend or risk to subjects.

Safety Topics of Interest

The following safety topics of interest will be monitored during the study:

- Serious infections, opportunistic infections, fungal infection, and tuberculosis (TB);
- Malignancies;
- Hypersensitivity reactions;
- Psychiatric adverse reactions such as suicidal ideations or attempt, abnormal/vivid dreams, or nightmares; and
- Neurological events.

Adverse Event Severity and Relationship to Study Drug

The investigator will rate the severity of each AE according to the National Cancer Institute Common Terminology Criteria for Adverse Events (NCI CTCAE Version 5.0).

The investigator will use the following definitions to assess the relationship of the AE to the use of study drug:

Reasonable Possibility	After consideration of factors including timing of the event, biologic plausibility, clinical judgment, and potential alternative causes, there is sufficient evidence (information) to suggest a causal relationship.
No Reasonable Possibility	After consideration of factors including timing of the event, biologic plausibility, clinical judgment, and potential alternative causes, there is insufficient evidence (information) to suggest a causal relationship.

Pregnancy

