3.15 Unscheduled Visits

An Unscheduled Visit should be performed when the subject comes in for a medical visit for evaluation and assessment. During Unscheduled Visits, blood and urine samples may be obtained for the laboratory tests listed in Section 3.13 or for other tests at the investigator's discretion; physical examination (including neurological examination) may be performed at the investigator's discretion.

Visits for dispensing new study drug in case of temperature excursion, loss or damage are not considered an Unscheduled Visit. In addition, visits to only retest a lab will not be considered an Unscheduled Visit.

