4 SAFETY MANUAL

4.1 Methods and Timing of Safety Assessment

All serious and nonserious adverse events that could be related to study procedures will be collected from the time the subject signed the study-specific informed consent until study drug administration. From the time of study drug administration until 30 days after the last dose of study drug or study treatment, all nonserious and serious adverse events will be collected whether solicited or spontaneously reported by the subject. After 30 days following the last dose of study drug or completion of study treatment only spontaneously reported SAEs will be collected (nonserious AEs will not be collected).

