10.2.1 Treatment-Emergent Adverse Events

Treatment-emergent adverse events (TEAEs) are defined as any AE with an onset date that is after the first dose of study treatment and no more than 30 days after the last dose of study treatment. Events where the onset date is the same as the study treatment start date are assumed to be treatment-emergent. All treatment-emergent AEs will be summarized overall, as well as by primary MedDRA SOC and Preferred Term. The SOCs will be presented in alphabetical order, and the PTs will be presented in alphabetical order within each SOC. The number and percentage of subjects experiencing treatment-emergent AEs will be summarized.

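### Minor: the ±7-day window on the 30-Day Follow-Up lets the last scheduled adverse-event enquiry, for subjects dosed to about Week 16, fall up to 7 days before the 30-day collection period ends

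*Protocol*

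**What the plan says.** Three places set the period over which AEs count, and all use 30 days.

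- Protocol 6.1: "All adverse events reported from the time of study drug administration until 30 days after discontinuation of study drug administration will be collected", whether asked for or volunteered.
- Operations Manual 4.1 (Protocol Appendix F) repeats that period. For the time after it, the manual says that "only spontaneously reported SAEs will be collected (nonserious AEs will not be collected".
- SAP 10.2.1 counts an AE as treatment-emergent by its onset date, up to "no more than 30 days after the last dose of study treatment".

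The schedule is set separately. Protocol 4.1 describes "a 30-day follow up period from the last dose of study drug", and the final column of Appendix D is headed "30- Day Follow-Up (± 7 days". AE monitoring is ticked in that column, and Operations Manual 2.1 lists an AE assessment for the contact. For subjects who withdraw, Protocol 5.6 says that a 30-day call "may be completed to ensure all treatment-emergent AEs/serious adverse events (SAE) have been resolved".

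The plan also has safeguards outside the schedule. Protocol 6.1 states: "All AEs will be followed to a satisfactory conclusion". Operations Manual 3.15 states: "An Unscheduled Visit should be performed when the subject comes in for a medical visit for evaluation and assessment", and Operations Manual 2.1 includes an AE assessment at such a visit. Serious AEs go to the sponsor within 24 hours of the site learning of them.

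**The concern.** The window is symmetric around the day on which the collection period ends. A site can therefore comply with Appendix D and ask its last AE question before that period is over. I found no text that bars a contact before day 30, or that schedules a later one for a subject dosed to about Week 16.

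Safety is part of the stated primary objective (Protocol 3.1), and the TEAE tables apply the same 30-day limit to every subject. For a subject seen early, the last few days of that period are never asked about, for no reason other than when the contact was booked.

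**Working it through.** **Inputs.** Target day 30 after the last dose, window ±7 days (Appendix D, Protocol 4.1). End of AE collection and TEAE counting: day 30 (Protocol 6.1, Operations Manual 4.1, SAP 10.2.1). Treatment: 16 weeks = 112 days. Planned subjects: about 40. The 30-day limit is the same in all three places, so there is no conflict over the period itself.

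**Allowed contact days.** 30 − 7 = 23 to 30 + 7 = 37. That is 15 days: 7 before day 30, day 30 itself, and 7 after.

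**Days left without a scheduled enquiry.** Gap = max(0, 30 − contact day).

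- Day 23: 30 − 23 = 7 days (days 24 to 30).
- Day 29: 30 − 29 = 1 day.
- Days 30 to 37: 0 days.

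**Largest share for one subject.** 7/30 = 23.3% of the off-drug period. The TEAE window for a subject dosed to Week 16 is 112 + 30 = 142 days, and 7/142 = 4.9%.

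**Ceiling for the study.** 40 × 7 = 280 of 40 × 142 = 5,680 person-days, again 4.9%. This needs all 40 subjects to be dosed to Week 16 and seen on day 23.

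**A milder illustration.** If contacts were spread evenly over the 15 allowed days (an assumption), the mean gap would be (7+6+5+4+3+2+1)/15 = 28/15 = 1.9 days, or 1.3% of 142. Contacts clustered near day 30 would give less. The documents do not give the actual contact days.

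**Who is affected.** Subjects who stop drug early but stay in the study keep their scheduled visits (Protocol 5.6), so the Week 16 visit may be the later AE enquiry. With that visit on about day 112, the largest gap is max(0, 30 − max(23, 112 − last-dose day)).

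- Last dose on day 89 or later: 112 − 89 = 23, so the full 7 days is possible.
- Last dose by day 82: 112 − 82 = 30, so the gap is 0.
- With the Week 16 visit at the early edge of its ±3-day window (day 109), the thresholds become 109 − 23 = day 86 and 109 − 30 = day 79.

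**After the fix.** With days 30 to 37 allowed, the gap is 0 on every allowed day, and 8 scheduling days remain.

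**The case against.** The strongest reply is that no rule contradicts another. Collection runs to day 30 however an event comes to light, and the TEAE rule works on onset date. A volunteered event starting on day 28 is therefore recorded and counted even if the contact was on day 23. That stands. A reader might infer that an early contact closes AE collection, but the documents do not say so.

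The safeguards also stand. What they leave is a new, nonserious, off-drug event in the last 1 to 7 days that prompts no medical visit and is not volunteered. The study is single-arm, so there is no between-arm difference in ascertainment. The safety analysis is descriptive, and the stopping review in Protocol 5.5 turns on related events of grade 3 or higher.

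A reader might take 280 of 5,680 person-days as an expected loss. It is a ceiling. The SAP reports numbers and percentages of subjects with events, not rates per person-time, so the fraction maps to no planned estimate.

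A reader might also infer that the late half of the window fails. Protocol 6.1 speaks of AEs reported until day 30, and Operations Manual 4.1 stops collecting nonserious AEs after that. Taken literally, a nonserious AE that starts on day 28 and is elicited on day 33 would go unrecorded. The documents make that reading unlikely: they require an AE assessment at a contact allowed to day 37, and the TEAE rule goes by onset. The wording merits clarification but is not a second gap.

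The reply does not remove the main point: days 23 to 29 are permitted, and no later enquiry is scheduled for these subjects.

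**Conclusion.** The point holds as a minor, inexpensive improvement. Appendix D permits a gap of up to 7 days in solicited AE ascertainment for a subject dosed to about Week 16. The gap is 0 if the contact is on day 30 or later. No number of missed TEAEs can be claimed, and neither the primary efficacy analysis nor the sample size is affected.

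This rests on counting the follow-up from the last dose, as Protocol 4.1 does, and on a Week 16 visit at about day 112. The size for the study as a whole cannot be estimated without the actual contact days.

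**What to change.** In Appendix D, change the 30-Day Follow-Up window from ±7 days to 0/+7 days (days 30 to 37 after the last dose), prospectively. As a clarification only, state in Protocol 6.1 and Operations Manual 4.1 that AEs with onset through day 30 are recorded when elicited at that contact.

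The cost is a minor amendment with ethics committee approval (Protocol 8.1) and a scheduling range of 8 days instead of 15. The latest allowed day stays at 37, though follow-up ends slightly later for subjects who would have been seen on days 23 to 29.

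The documents do not give subject status. SAP version 3.0 is dated 31 October 2024, so a prospective change may reach few subjects. If no subject is still in follow-up, skip the amendment and report with the TEAE tables how many subjects had their last AE contact before day 30. That should need only the visit and dosing dates.
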